4.1. Time Windows for Follow-up Period

For IOP and number of IOP-lowering medications only, data from the latest clinic visit recorded within the following time windows will be used in the analysis:

- Month 12: data between Month 9 and Month 15 after XEN 45 Gel Stent implantation
- Month 24: data between Month 21 and Month 27 after XEN 45 Gel Stent implantation
- Month 36: data between Month 33 and Month 39 after XEN 45 Gel Stent implantation
- Month 48: data between Month 45 and Month 51 after XEN 45 Gel Stent implantation
- >Month 51 after XEN 45 Gel Stent implantation

Unless otherwise specified, all other retrospective data (See Section 1.8) collected from baseline until the last visit will be categorised into the following groups for the follow-up period analyses, based on latest available data within the time window:

- ≤ 12 months: data ≤ 12 months after XEN 45 Gel Stent implantation
- > 12 to ≤ 24 months: data > 12 to ≤ 24 months after XEN 45 Gel Stent implantation
- > 24 to ≤ 36 months: data > 24 to ≤ 36 months after XEN 45 Gel Stent implantation
- > 36 to ≤ 48 months: data > 36 to ≤ 48 months after XEN 45 Gel Stent implantation
- >48 months: data from >48 months after XEN 45 Gel Stent implantation to end of study period

Needling procedures will be summarised descriptively within the following time-windows:

- < 3 months: data < 3 months after XEN 45 Gel Stent implantation
- > 6 to ≤ 12 months: data > 6 to ≤ 12 months after XEN 45 Gel Stent implantation
- > 12 to ≤ 24 months: data > 12 to ≤ 24 months after XEN 45 Gel Stent implantation
- > 24 to ≤ 36 months: data > 24 to ≤ 36 months after XEN 45 Gel Stent implantation
- > 36 to ≤ 48 months: data > 36 to ≤ 48 months after XEN 45 Gel Stent implantation
- > 48 months: data > 48 months after XEN 45 Gel Stent implantation

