10.7 Needling Procedures

Date of needling procedures performed on the bleb after XEN 45 Gel Stent implantation will be collected throughout the study period.

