14.2.3 Disease Progression

Ocular medical history, IOP lowering medications and needling procedures will be summarized descriptively. Visual field exam and BCVA will be summarized descriptively at baseline and for all time points of interest.

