3.4. Missing Data

The eCRF is designed to ensure that no questions are left unanswered. If 'unknown' is selected, this will be included as such in the results and tabulated for all variables. Central tendencies will not be measured for continuous unknown data, only counts and percentages will be recorded.

In some cases, imputation of unknown variables may be conducted if the variable is to be used in calculations for another variable or analysis. For example, the eCRF allows some dates to be incomplete (i.e. day is unknown) if it is not available in the medical chart. This may impact accurate calculation of durations, resulting in an imputation needing to be made. If the day is missing, the date will be imputed as the 15th of the month, except in cases where this would lead to a negative duration, in which case the 1st or last day of the month will be used (whichever addresses the negative duration). No imputation will be made for missing month/year; these are classified as date unknown within the eCRF. All imputed values will be documented and presented as footnotes in the result tables.

4. Planned Analyses

The analyses detailed below will be performed to meet the project objectives. There will be two analysis populations specified for the analyses to be conducted:

- The **Effectiveness Population** consists of all eligible study eyes in the population except in instances when a patient has contributed both eligible eyes in the study, then only the eye that received the Xen-45 implant first will be selected; this eye will be presented in tables as the 'primary eye'. All results tables in the Effectiveness Population will include stratified results presenting data for the primary eye, as well as data on all included patient eyes (even if both eyes from a single patient are included).
- The **Safety Population** consists of all eligible study eyes in the population.

All results tables will be stratified by Xen-45 implant only, implant plus phacoemulsification, and total population. Sensitivity analyses will be conducted to assess study results in the 'second eye' (i.e. not the primary eye as described above), for patients where both eyes were included. The sensitivity analyses will focus on the tables conducted using the Effectiveness Population.

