4.3. Disease progression

Ocular medical history will be summarised descriptively in the Safety Population overall and not by the time windows specified. Needling procedures will be summarized in the Safety Population by the time windows indicated in Section 4.1. Anti-metabolite/anti-fibrotic use will be described during the stent implantation, during conjunctiva bleb revision (if applicable), during needling procedures (if applicable), and also when used alone. Anti-metabolite/anti-fibrotic use during needling procedures will be determined based on the date of each anti-metabolite/anti-fibrotic use and date of the needling procedure; the same date assumes that the anti-metabolite/anti-fibrotic was used in conjunction with the needling procedure. IOP lowering medications (oral) will be described at baseline and post-implantation in the Effectiveness Population by class of medication (carbonic anhydrase inhibitors or alpha-agonist hypotensive agent). Visual field exam will be summarised descriptively at baseline and for all time points of interest (as described in Section 4.1) in the Safety Population. All BCVA values will be converted to logarithm of the minimum angle of resolution (logMAR) units.³ To do this, Snellen values will be converted by taking the negative base 10 logarithm of the decimal. ETDRS letters will be converted to approximate Snellen scores by the following formula.

$$\text{Snellen} \cong \exp \left\{ \frac{1}{50} (\text{ETDRS} - 85) \right\}.$$

This will then be converted into logMAR units using the negative base 10 logarithm of the decimal as above. Any non-numerical BCVA values (i.e. including count fingers, hand movement, light perception and non-light perception) will also be converted to logMAR units as described below:⁴

Non-numerical BCVA value	LogMAR
Count fingers (CF)	1.8
Hand movement (HM)	2.3

Light perception (LP)	2.8
No light perception (NLP)	3.0

4.4. Change in IOP and number of topical IOP-lowering medications after XEN 45 gel stent implantation

Change in IOP from medicated baseline and change in the number of topical IOP-lowering medications will be summarised. Change in number of IOP-lowering medications will be made by examining the class of the medication as follows:

- Beta Blocking Agents
- Carbonic Anhydrase Inhibitors
- Parasympathomimetics
- Prostaglandin Analogues
- Sympathomimetics In Glaucoma Therapy

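### The needling windows in SAP 4.1 leave out Months 3 to 6, so procedures in that period have no row in the needling table

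*SAP*

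**What the plan says.** SAP 4.1 sets three groups of windows: one for IOP and number of IOP-lowering medications, a default group for other data, and a separate group for needling.

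The needling group begins with "< 3 months: data < 3 months after XEN 45 Gel Stent implantation". The next entry is "> 6 to ≤ 12 months: data > 6 to ≤ 12 months after XEN 45 Gel Stent implantation". It then continues in yearly steps to Month 48, with an open last row after Month 48.

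The default group is introduced by "Unless otherwise specified, all other retrospective data (See Section 1.8" and begins with a single row for everything up to and including Month 12.

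SAP 4.3 ties the needling summary to the 4.1 list: "Needling procedures will be summarized in the Safety Population by the time windows indicated in Section 4.1". It also plans a summary of anti-metabolite or anti-fibrotic use "during conjunctiva bleb revision (if applicable), during needling procedures (if applicable"), matched to needling by date.

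On the protocol side, section 10.7 says that needling dates "will be collected throughout the study period", and section 14.2.3 says: "Ocular medical history, IOP lowering medications and needling procedures will be summarized descriptively". Neither restricts the period.

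SAP section 4 adds that "All results tables will be stratified by Xen-45 implant only, implant plus phacoemulsification, and total population".

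**The concern.** The needling list divides the first year more finely than the default list does, yet it omits the middle of that year. No reason is given, and the list reads as a drafting slip. A programmer who follows it exactly has nowhere to put a needling at, say, Month 4. The choice is then to drop the event or to create an unplanned row once the data are in hand.

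This table is the only needling summary that SAP 4.3 names. If Month 3 to 6 procedures are dropped, first-year needling is under-reported. Where the table counts procedures, its rows will not add up to the dated needlings in the database. The omission repeats in each stratum, because every results table is split by procedure type. The SAP would also report less than the protocol's unrestricted plan to summarise needling.

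**Working it through.** The plan states no figure for this point, so there is none to reproduce. The check is whether the listed windows cover all of follow-up.

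**Inputs (SAP 4.1).** Writing *t* for months since implantation, the needling rows are:

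| Row | Interval |
|---|---|
| 1 | [0, 3) |
| 2 | (6, 12] |
| 3 | (12, 24] |
| 4 | (24, 36] |
| 5 | (36, 48] |
| 6 | (48, ∞) |

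**Coverage.** The union is [0, 3) ∪ (6, ∞), so the uncovered set is [3, 6]. Month 3 is out because row 1 is strictly below 3. Month 6 is out because row 2 is strictly above 6. A check of every time from 0 to 57 months in steps of 0.01 found 3.00 to 6.00 uncovered, no other gap, and no time in two rows.

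**Comparison.** The default list, [0, 12], (12, 24], (24, 36], (36, 48], (48, ∞), passes the same check with no gap and no overlap. The fault is confined to the needling list.

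**Does another rule fill the gap?**
- The default list applies only where nothing else is specified, and needling is specified directly below it.
- SAP 4.3 sends needling to the 4.1 windows and gives no all-period total. The sentence before it does ask for an overall summary of ocular history, so the SAP says so where it wants one.
- Needling is not a named event in the AESI list in SAP 1.8, and it is listed there separately from secondary surgical intervention. Those tables are not designed to recover it.
- The anti-metabolite summary could show only needlings with an agent recorded on the same date.
- Conjunctival bleb revision is a separate item in SAP 4.3 and is not affected.

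**Size in time.**
- Length of gap: 6 − 3 = 3 months, that is 3 of the first 12.
- Eye-months with no row at the planned 150 eyes (SAP 2): 150 × 3 = 450 at most.
- First-year eye-months if every eye is followed for 12 months: 150 × 12 = 1,800.
- Share under full follow-up: 450 / 1,800 = 25%.

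Eyes lost, or censored at a secondary surgical intervention, reduce these totals. The 25% is not a ceiling: eyes that leave after Month 6 shrink the denominator but not the numerator. Neither document gives a needling rate or timing, so these figures cannot be turned into a count of procedures.

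**After the fix.** With [3, 6] added, every time from 0 to 57 months falls in exactly one row.

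**The case against.** The strongest case against concerns weight, since the gap itself is plain on the page.

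- **Needling is minor in this plan.** It is not in the objectives, outcome variables or named AESIs. It is a descriptive item under disease progression, with no test attached. The dates are collected, so the omission can be repaired when the table is built. This stands, and it limits the point to one table. It does not remove the need to correct a rule that, applied exactly, drops events from a planned result.
- **A bullet may have been lost when the PDF was read.** This cannot be fully excluded, and there are stray empty bullets in the AESI lists of both documents. The needling list reads as unbroken, however, and nothing marks a removal. A look at the signed SAP settles it.
- **Adding up depends on the counting unit.** The SAP does not say whether the table counts procedures or eyes with at least one needling. If it counts eyes, one eye can appear in several rows, and the rows need not sum even with complete windows. If it counts procedures, those with an unknown month or year still fit no row. Both remarks are correct. The fix ensures only that every needling with a usable date has a row.
- **The protocol's commitment is brief.** Section 14.2.3 is one line, and section 14.2 leaves detail to the SAP. That weakens any claim of a formal conflict. Still, choosing windows is different from leaving a quarter of the first year out of them without a reason.
- **Eye-months do not measure impact.** Agreed. They describe only the time without a row.

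**Conclusion.** The point holds. As printed, the needling windows omit Month 3 to Month 6 inclusive, and no other rule in the SAP assigns those procedures to a needling row. Three of the first 12 months are affected, in all three strata. The number of procedures omitted is not estimable from the documents.

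The conclusion assumes that the printed list is complete and that the table is programmed as written. The effect is confined to the windowed needling table. The underlying data, the primary analysis of IOP and medications, and the qualified and complete success outcomes are untouched. It should be corrected before the tables are produced.

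**What to change.** In SAP 4.1, add one needling window, ≥ 3 to ≤ 6 months, and leave the other rows as they are. This is the smallest change. If the sponsor prefers the same boundary style throughout, the equivalent is ≤ 3, > 3 to ≤ 6, then > 6 to ≤ 12; Month 3 exactly then moves into the first row.

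Optionally, add an any-time row as a check on totals, and state whether the table counts procedures or eyes, since that decides whether the rows should sum to it.

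The cost is one bullet in the SAP and one row in the needling table, or two rows with the optional check. No new data are needed, because needling dates are already collected.

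If the signed SAP already contains the row, only the programmed table needs checking against it.

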4.2. Disposition and patients' characteristics

Number and percentage of eyes in both the Effectiveness and Safety Analysis Populations will be described. Demographic characteristics will be summarised descriptively for all included patients in the study.

[figure not shown]
4.3. Disease progression

Ocular medical history will be summarised descriptively in the Safety Population overall and not by the time windows specified. Needling procedures will be summarized in the Safety Population by the time windows indicated in Section 4.1. Anti-metabolite/anti-fibrotic use will be described during the stent implantation, during conjunctiva bleb revision (if applicable), during needling procedures (if applicable), and also when used alone. Anti-metabolite/anti-fibrotic use during needling procedures will be determined based on the date of each anti-metabolite/anti-fibrotic use and date of the needling procedure; the same date assumes that the anti-metabolite/anti-fibrotic was used in conjunction with the needling procedure. IOP lowering medications (oral) will be described at baseline and post-implantation in the Effectiveness Population by class of medication (carbonic anhydrase inhibitors or alpha-agonist hypotensive agent). Visual field exam will be summarised descriptively at baseline and for all time points of interest (as described in Section 4.1) in the Safety Population. All BCVA values will be converted to logarithm of the minimum angle of resolution (logMAR) units.³ To do this, Snellen values will be converted by taking the negative base 10 logarithm of the decimal. ETDRS letters will be converted to approximate Snellen scores by the following formula.

$$\text{Snellen} \cong \exp \left\{ \frac{1}{50} (\text{ETDRS} - 85) \right\}.$$

This will then be converted into logMAR units using the negative base 10 logarithm of the decimal as above. Any non-numerical BCVA values (i.e. including count fingers, hand movement, light perception and non-light perception) will also be converted to logMAR units as described below:⁴

Non-numerical BCVA value	LogMAR
Count fingers (CF)	1.8
Hand movement (HM)	2.3

Light perception (LP)	2.8
No light perception (NLP)	3.0

4.4. Change in IOP and number of topical IOP-lowering medications after XEN 45 gel stent implantation

Change in IOP from medicated baseline and change in the number of topical IOP-lowering medications will be summarised. Change in number of IOP-lowering medications will be made by examining the class of the medication as follows:

- Beta Blocking Agents
- Carbonic Anhydrase Inhibitors
- Parasympathomimetics
- Prostaglandin Analogues
- Sympathomimetics In Glaucoma Therapy

These will be compared to baseline and will be summarised descriptively at months 12, 24, 36 and 48 after XEN 45 Gel Stent implantation in eyes from the Effectiveness Population. Analyses will only include those with available data at each of the time points of interest and those who were not treated with Diamox on the day when decision was taken to implant XEN 45 Gel Stent.

A paired t-test will be applied for statistical analysis in comparing the difference between post baseline to baseline values. The assumptions of the test are as follows:

- No significant outliers in the differences between time points (which can be tested by a scatter plot of the data)
- The distribution of the differences in the dependent variable between the two time points should approximately follow a normal distribution (which can be tested through the Shapiro-Wilk test)
- The dependent variable is measured on a continuous scale

If the assumptions of the t-test are heavily violated then the non-parametric analogue (Wilcoxon Signed-Rank test) should be used to test the difference between time points.

4.4.1. Success over the long term of following implantation of the XEN 45 Gel Stent

Number and proportion of eyes achieving a 20% reduction in IOP from medicated baseline, and number and proportion of eyes with an IOP between 6 and 18 mmHg, IOP between 6 and 17 mmHg, ..., down to IOP between 6 and 12 mmHg will be described by the time-windows described in Section 4.1 in eyes from the Effectiveness Population that did not undergo SSI for glaucoma, and were not treated with Diamox on the day when decision was taken to implant XEN 45 Gel Stent.

The number and proportion of eyes achieving qualified or complete success at each time point of interest (i.e. 12, 24, 36, 48 and >51 months) after XEN 45 Gel Stent implantation will be summarised descriptively. Analyses will be conducted in the Effectiveness Population.

The time from XEN 45 Gel Stent implantation to SSI for glaucoma will be described using Kaplan Meier curves.

4.5. Safety over the long term following implantation of the XEN 45 Gel Stent

Surgical complications and post-operative AESIs will be summarised descriptively using frequencies and percentages.

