14 STATISTICAL METHODS

14.1 Sample Size

To answer study primary objective, this chart review study plans to accrue a minimum of 60 study eyes that have had at least 3 years of follow-up data without a SSI for glaucoma after the initial implant with XEN 45 Gel Stent.

Data from the Allergan study MS-001 demonstrated that the mean IOP reduction from baseline differed slightly among the 7 visits (see below) in the 24-month post-implant period. The absence of a clear waning-out trend suggests that the effect of XEN 45 Gel Stent implantation on IOP reduction may last to Month 36 and beyond. The minimum mean reduction (negative sign stands for reduction) in IOP among the visits was -5.6 (± 6.32) mmHg, which was observed at Month 3. This value was then taken as an initial estimate for the mean reduction projected for Month 36. The 95% confidence interval (CI) of the projected mean reduction afforded by a sample of 60 study eyes is -7.2 to -4.0 mmHg. That is, the half-length of the interval is 1.6 mmHg, which provides a reasonable precision for the estimate of the projected mean reduction in IOP.

Table 4 Result from the MS-001 Study

Visit	Number of study eyes	Mean (SD) change in IOP from medicated baseline (mmHg)
Month 1	167	-6.3 (6.41)
Month 3	167	-5.6 (6.32)
Month 6	168	-6.4 (4.92)
Month 9	134	-6.1 (5.68)
Month 12	161	-6.7 (5.41)
Month 18	149	-7.1 (5.10)
Month 24	149	-6.2 (4.94)

The MS-001 study enrolled 199 patients (218 study eyes). In this study, patients' discontinuation rate tended to be linear over the 2-year follow-up period, with an overall study discontinuation rate of approximately 20%. Using data from the MS-001 study, it could be assumed that 30% of the eyes selected for this study have less than 3 years of follow-up data. Taking into consideration that MS-001 study was a clinical trial and that patient retention rate is expected to be lower in a real-world setting, the study will aim to select 150 eyes to ensure obtaining a minimum of 60 eyes with at least 3 years of follow-up data.

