1.7. Study Population

The study population includes patients with one or both eyes with open angle glaucoma that underwent XEN 45 Gel Stent implantation.

Patients meeting the following criteria are eligible for participation in the study:

1. Eye treated with XEN 45 Gel Stent for open angle glaucoma as a standalone procedure or in combination with phacoemulsification
2. XEN 45 Gel Stent was implanted between 1 January 2014 and 1 October 2015
3. Charts contain minimum required data (age, gender, IOP at baseline until last visit, number of topical IOP-lowering medications prescribed for the study eye from baseline until last visit, date of the SSI for glaucoma if applicable)

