1.8. Data Collection

Data are being collected from patients' medical records using an eCRF on the Dacima platform. The eCRF includes edit and range checks to minimize the amount of missing or invalid data.

[figure not shown]
The schedule for data collection is presented below:

Data Collected	Baseline[a]	XEN 45 Gel Stent Implantation	Study Period[b]
Eligibility Assessment	X		
Demography	X		
Ocular and Glaucoma Medical History	X		
Surgery-related data		X	
Number of IOP-lowering medications	X		X
Visual field exam	X		X
Intraocular pressure	X		X
Best corrected visual acuity	X		X
Needling procedures			X
Secondary surgical intervention for glaucoma			X
Adverse events of special interest			X

IOP=intra-ocular pressure.

[figure not shown]
[a] Baseline is defined as the day when the decision was made to implant XEN 45 Gel Stent.

[b] The study period is defined as the period between XEN 45 Gel Stent implantation and 1 October 2018. For each eye selected, all retrospective data available from baseline until 1 October 2018 or until the date on which the patient received a SSI for glaucoma, whichever occurs first, are from existing medical records.

Data collected includes:

- Demographics
- Selected eye characteristics (oculus dexter vs. oculus sinister), along with information about whether patient's other eye was also selected.
- Ocular and Glaucoma Medical History
- Surgery-Related Data
 - Use of anti-metabolite and/or anti-fibrotic
 - Procedure performed (i.e., XEN 45 Gel Stent implantation alone or phacoemulsification + XEN 45 Gel Stent implantation)
 - XEN 45 Gel Stent and cataract-related complications
- Intraocular Pressure Data
 - IOP-related data, i.e. IOP and number of topical IOP-lowering medications
- Visual Field Exam
- Best Corrected Visual Acuity (BCVA), including method used
- Needling Procedures
- Secondary Surgical Intervention (nature and date, if applicable)
- Adverse events of special interest (AESI):
 - Anterior chamber defects:
 - Shallow with peripheral iridocorneal touch
 - Flat with irido-corneal touch extending to the pupil
 - Bleb leak
 - Blebitis
 - Choroidal effusion, hemorrhage or mixed effusion hemorrhage recorded as follows:
 - Extending posterior to the equator
 - Obscuring disc or macula
 - With choroids touching in the centre of the eye
 - Persistent choroidal effusion, hemorrhage or mixed effusion hemorrhage occurring > 30 days post-operation
 - Corneal oedema:
 - Transient corneal decompensation / edema (<30 days)

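### Visual field and BCVA are planned only as levels per window, so differences between rows mix within-eye change with a change in which eyes contribute; SAP 4.3 should add paired change from baseline.

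*SAP*

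**What the plan says.** Protocol 14.2.3, headed Disease Progression, states: "Visual field exam and BCVA will be summarized descriptively at baseline and for all time points of interest". SAP 4.3, under the same heading, repeats this for visual field alone, in the Safety Population: "Visual field exam will be summarised descriptively at baseline and for all time points of interest". For BCVA, SAP 4.3 gives conversion rules ("All BCVA values will be converted to logarithm of the minimum angle of resolution (logMAR) units") but names no summary statistic, population or change.

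SAP 4.4 treats the performance outcomes differently. There, "Change in IOP from medicated baseline and change in the number of topical IOP-lowering medications will be summarised", with a paired test, in eyes that have data at the time point.

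Three other provisions decide which eyes appear in each visual field or BCVA row:
- SAP 4.1 assigns one value per window, "based on latest available data within the time window".
- SAP 1.8 extracts data to the cutoff or "until the date on which the patient received a SSI for glaucoma, whichever occurs first".
- Protocol 8.2.3 and SAP 1.7 list the minimum required data. Visual field and BCVA are not among them.

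On loss of follow-up, Protocol 14.1 says "it could be assumed that 30% of the eyes selected for this study have less than 3 years of follow-up data", and then plans 150 eyes to secure at least 60 with 3 years of data.

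**The concern.** Readers of a disease progression table will compare the baseline row with the later rows. Those rows describe different sets of eyes. If the eyes that drop out had worse fields at baseline, the later mean is pulled upward by their absence, and a real decline looks smaller or disappears. If the eyes that drop out were healthier, the decline is exaggerated. The table as planned gives no means of telling these cases apart, because it never shows the baseline of the eyes that remain.

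Both documents name the prevention of further loss of functional vision as the goal of glaucoma treatment, and the study is intended for publication, so these tables are likely to be read as evidence on that question. The baseline and follow-up values needed for a paired comparison are already in the collection schedule.

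**Working it through.** **The plan's own figure.** Protocol 14.1 reports about 20% discontinuation over 2 years in MS-001, roughly linear. Extended to 3 years: 20% × 3/2 = 30%, which reproduces the stated figure and leaves 150 × 0.70 = 105 eyes. The minimum of 60 corresponds to 60/150 = 40% retained, or 60% lost. The documents give no level, SD or rate of change for mean deviation, and no precision for visual field or BCVA.

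**Why the rows differ.** Eligible eyes satisfy "XEN 45 Gel Stent was implanted between 1 January 2014 and 1 October 2015", and the cutoff is 1 October 2018, so potential follow-up runs from 36 to 57 months. Every eye could in principle reach month 36, but the latest implants cannot supply values much beyond it. SSI and loss to follow-up remove eyes earlier. A missing field or BCVA removes an eye from a row even while it is still followed.

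**Formula.** Let f be the fraction of eyes with a baseline value that have no later value, d the amount (dB) by which those eyes were worse at baseline, m the baseline mean of the retained eyes, and Δ their true mean change.
- Baseline row: (1 − f)·m + f·(m − d) = m − f·d
- Later row: m + Δ
- Apparent change: Δ + f·d

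**Numbers.** Δ = -1.5 dB and the values of d are assumptions. The values f = 0.30 and 0.60 come from Protocol 14.1.

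| d (dB) | f = 0.30 | f = 0.60 |
|---|---|---|
| 0 | -1.5 | -1.5 |
| 1 | -1.5 + 0.3 = -1.2 | -1.5 + 0.6 = -0.9 |
| 3 | -1.5 + 0.9 = -0.6 | -1.5 + 1.8 = +0.3 |
| 5 | -1.5 + 1.5 = 0.0 | -1.5 + 3.0 = +1.5 |

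The decline is fully hidden when d = 1.5/f: 5 dB at 30% loss and 2.5 dB at 60%. For a true change of -0.9 dB these gaps are 3.0 and 1.5 dB; for -3.0 dB they are 10 and 5 dB. If the lost eyes were 3 dB healthier (d = -3), the tables would show -1.5 − 0.9 = -2.4 dB and -1.5 − 1.8 = -3.3 dB.

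For BCVA the same identity holds with the sign turned, since a higher logMAR is worse.

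**Check by simulation** (150 eyes, 4,000 runs; assumed baseline SD 6 dB, correlation 0.5 between baseline mean deviation and retention, true change -1.5 dB). The row difference averaged +1.4 dB at 40% retention and 0.0 dB at 70%. The paired change in retained eyes averaged -1.5 dB in both. Change was generated independently of retention, so this shows only that pairing removes the baseline composition effect.

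**The case against.** Visual field and BCVA appear in neither the objectives nor the outcome variables of either document. Performance is IOP, medications and success; safety is adverse events of special interest, which already capture some visual harm (clinical hypotony with loss of 2 lines or more, and events leading to permanent visual impairment). The tables also report the proportion with unknown data, so missingness is visible. All of this stands and limits the weight of the point. It does not make the rows comparable. The protocol's general statement in 14.2.1 about figures of change over time names neither measure and does not commit to within-eye change.

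Four stronger readings are tempting, and the documents do not support them:
- A reader might infer that the tables will show improvement while eyes worsen. That needs a sizeable baseline gap, and no passage links field severity to loss. At 30% loss, gaps of 1 to 3 dB dilute the decline but leave it visible.
- A reader might infer that 60% of eyes will be absent from the Year 3 row. It is an upper bound on the loss of follow-up tolerated by Year 3. The SAP counts its 60 as independent eyes without SSI, so a second eye may lie outside the 60 yet remain in the Safety Population. Also, the visual field window is >24 to ≤36 months, so an eye last seen at month 30 counts as short of 3 years but still supplies a value.
- A reader might take the baseline row to cover all eyes. It covers only eyes with a value, because neither measure is required for selection. The formula above therefore applies to eyes with a baseline value.
- A reader might take paired change as an unbiased measure of progression. It still describes only the eyes that remain observed.

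**Conclusion.** The omission is real. Neither document plans a within-eye change, slope or same-eye comparison for visual field or BCVA, and the SAP names no BCVA summary at all. The composition of the rows will change, for reasons set out in the plan itself. Whether this biases the comparison, and in which direction, cannot be known from the documents. For an assumed true change of -1.5 dB and gaps of 0 to 5 dB, the apparent change ranges from -1.5 to 0.0 dB at 30% loss and from -1.5 to +1.5 dB at 60% loss. With no link between loss and severity there is no bias; with loss of healthier eyes it runs the other way. This is a worthwhile correction to supportive analyses, and it leaves the primary IOP objective untouched.

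**What to change.** In SAP 4.3, for each window in 4.1:
- Add the within-eye change from baseline in mean deviation and in logMAR BCVA, in eyes with both values.
- In the same row show n and the baseline mean of those same eyes, stratified by procedure as the SAP already plans for all tables.
- State the population and summary statistics for BCVA, which Protocol 14.2.3 promises and the SAP omits.
- Keep the raw levels as background.
- State that paired change describes only eyes still observed and does not remove bias if the eyes that leave progress faster. Showing the baseline mean of eyes with no later value would let readers judge the gap directly.

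The cost is SAP wording and extra table columns. No new data are needed.
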